7.2 Study Exit

A Study Exit form will be completed for all subjects to document the reason for discontinuation or the date of study completion. In addition, subjects randomized to conservative care who express an interest in continuing in-home treatment with the Flexitouch Plus outside of the study will receive information from a Tactile Medical representative per standard procedure.

8.0 Risk Analysis and Adverse Events

Study subjects will be informed of any significant new findings that develop during the course of this study that may affect their willingness to continue participation. The investigator will oversee all safety aspects of the study, report all adverse events to the IRB, and ensure each subject is treated identically. Should a subject choose to terminate his or her participation in the study, he or she will be treated according to the standard of care that applies at the point of withdrawal.

8.1 Treatment Risks

Participants enrolled in this study are not expected to be at any higher or additional risk than those who use conservative care (compression garments), since IPC pressures do not exceed the pressures of static compression garments. IPC and static compression are minimal risk therapies with nominal complications or adverse events.

Likely:

- Local skin irritation
- Pain or discomfort
- Increased swelling

Less Likely:

- Cellulitis
- New or increased edema in the trunk and/or genital region

Highly Unlikely:

- Electric shock (if Flexitouch Plus device is not maintained or used properly)

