2.3 Device Description

2.3.1 Flexitouch Plus

The Flexitouch Plus (Tactile Medical™, Minneapolis, MN, USA) is a segmental, programmable, gradient advanced pneumatic compression device cleared for market in the USA (K170216, HCPCS code E0652). The device stimulates the lymphatic system by directing and moving excess fluid from an impaired lymphatic region to healthy regions where fluid can be absorbed and processed naturally by the body.

The system consists of two primary components: a controller unit and garments. The controller unit has connector outlets for garment hoses to plug into such that air can pass through the hoses and deliver treatment through sequential inflation and deflation of air chambers within the garments. The garments are constructed of nylon and have 27-32 chambers, depending upon garment size. The pressure setting is variable between “decreased,” “normal,” and “increased.”

The device is intended to provide in-home Manual Lymphatic Drainage (MLD) therapy for approximately 1 hour treatment duration. Indications for use include lymphedema, primary lymphedema, post-mastectomy edema, edema following trauma and sports injuries, post immobilization edema,

venous insufficiency, reducing wound healing time, and treatment and assistance in healing stasis dermatitis, venous stasis ulcers, or arterial and diabetic leg ulcers.

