6.7 Circumferential Measurements

Circumferential measurements will be taken at Baseline and Follow-up per standard care at the beginning of the visit at 4 sites on each leg (immediately after bioimpedance measurements and the removal of graduated compression), 1 site at the hips, and 1 site at the waist (for a total of 10 measurements) using a Gulick II tape measure. Sites include:

- Site 1=narrowest part of the ankle (right and left leg),
- Site 2=largest part of the calf (right and left leg),
- Site 3=top of knee cap for lower thigh (right and left leg),
- Site 4=thickest part of the upper thigh (right and left leg),
- Site 5=widest part of the hips, and
- Site 6=narrowest part of the waist.

Results will be recorded in centimeters on the respective data collection form.

At the Follow-up visit, additional circumferential measurements (including 4 sites on each leg, 1 site at the hips, and 1 site at the waist using a Gulick II tape measure) may be collected immediately after an approximately 60-minute in-clinic treatment with FT Plus. The measurements will be collected and recorded in the same fashion outlined above. .

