6.8 Physical Exam

The investigator (or designee) will perform a physical exam at Baseline and Follow-up to assess stage of lipedema and lymphedema, presence of edema at Sites 1-6 (where circumferential measurements were taken), and presence/absence of clinical symptoms. It is important to note that progression to lipo-lymphedema (lipedema with swelling), a requirement of this study, typically develops during Stage 2/3 of lipedema.

- Lipedema Stage:
 - Stage 1 = Smooth/normal skin surface with enlarged hypodermis/homogenous thickening of the subcutis.
 - Stage 2 = Bumpy, wave-like skin surface with indentations/nodular structures (masses, lipomas, angiolipomas) in the thickened subcutis.
 - Stage 3 = An increase in nodular changes/deformations and overhanging masses of tissue (especially on the thighs and around the knees).
- Lymphedema Stage:
 - Stage 0 = Latent or subclinical condition where swelling is not yet evident despite impaired lymph transport, subtle alterations in tissue fluid/composition, and changes in subjective symptoms.
 - Stage 1 = Early accumulation of fluid relatively high in protein content which subsides with limb elevation. Pitting may occur.
 - Stage 2 = Limb elevation alone rarely reduces the tissue swelling and pitting is manifest. Later in state 2, the limb may not pit as excess subcutaneous fat and fibrosis develop.

- Stage 3 = Symptoms of lymphostatic elephantiasis where pitting can be absent and trophic skin changes such as acanthosis, alterations in skin character and thickness, further deposition of fat and fibrosis, and warty overgrowths have developed.
- Edema at Sites 1-6:
 - None = No pitting
 - 1+ = Trace: Tissue returns to normal almost immediately
 - 2+ = Mild: Tissue returns after 15-59 seconds
 - 3+ = Moderate: Tissue returns after 1-2 minutes
 - 4+ = Severe: Tissue returns after > 2 minutes
 - NA = Tissue no longer pits due to induration

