6.11.4 Venous-, Lymphedema-, and Lipedema-Related Complications

Information about venous-, lymphedema-, and lipedema-related complications, including cellulitis, lymphangitis, deep vein thrombosis, skin breakdown, lymphorrhea, and lymphangiosarcoma, will be recorded on the Complication & Healthcare Utilization log.

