Appendix E. NRS Symptom & Pain Scale

VISUAL ANALOG SCALE TO EVALUATE SYMPTOM SEVERITY

ID: _____ **DATE:** _____

We are trying to find out about your lipo-lipedema symptoms. There are 12 items we would like you to respond to. This should take less than 1 minute of your time.

DIRECTIONS: You are asked to circle a number on each of the following lines to indicate how you are feeling RIGHT NOW about symptoms in your left and right leg (these questions are not asking about other parts of your body).

PLEASE COMPLETE THE FOLLOWING ITEMS WHILE THINKING ABOUT WHILE YOUR LEFT LEG:

- | | | | | | | | | | | | | |
|------------------|---|---|---|---|---|---|---|---|---|---|----|-----------------------------|
| 1. No swelling | 0 | 1 | 2 | 3 | 4 | 5 | 6 | 7 | 8 | 9 | 10 | Worst imaginable swelling |
| 2. No heaviness | 0 | 1 | 2 | 3 | 4 | 5 | 6 | 7 | 8 | 9 | 10 | Worst imaginable heaviness |
| 3. No pain | 0 | 1 | 2 | 3 | 4 | 5 | 6 | 7 | 8 | 9 | 10 | Worst imaginable pain |
| 4. No fatigue | 0 | 1 | 2 | 3 | 4 | 5 | 6 | 7 | 8 | 9 | 10 | Worst imaginable fatigue |
| 5. No tenderness | 0 | 1 | 2 | 3 | 4 | 5 | 6 | 7 | 8 | 9 | 10 | Worst imaginable tenderness |
| 6. No tightness | 0 | 1 | 2 | 3 | 4 | 5 | 6 | 7 | 8 | 9 | 10 | Worst imaginable tightness |

PLEASE COMPLETE THE FOLLOWING ITEMS WHILE THINKING ABOUT YOUR RIGHT LEG:

- | | | | | | | | | | | | | |
|----------------|---|---|---|---|---|---|---|---|---|---|----|---------------------------|
| 1. No swelling | 0 | 1 | 2 | 3 | 4 | 5 | 6 | 7 | 8 | 9 | 10 | Worst imaginable swelling |
|----------------|---|---|---|---|---|---|---|---|---|---|----|---------------------------|

VISUAL ANALOG SCALE TO EVALUATE SYMPTOM SEVERITY

ID: _____ **DATE:** _____

2. No heaviness	0	1	2	3	4	5	6	7	8	9	10	Worst imaginable heaviness
3. No pain	0	1	2	3	4	5	6	7	8	9	10	Worst imaginable pain
4. No fatigue	0	1	2	3	4	5	6	7	8	9	10	Worst imaginable fatigue
5. No tenderness	0	1	2	3	4	5	6	7	8	9	10	Worst imaginable tenderness
6. No tightness	0	1	2	3	4	5	6	7	8	9	10	Worst imaginable tightness

THANK YOU!

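### Genital edema, a named treatment risk, has no targeted item in the protocol, and trunk swelling is measured at both visits but planned only as an efficacy result

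*Combined protocol and SAP*

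**What the plan says.** **The risk.** Section 8.1 places "New or increased edema in the trunk and/or genital region" in its less-likely tier, together with cellulitis, and gives no rate. Section 2.3.1 describes the device as "directing and moving excess fluid from an impaired lymphatic region to healthy regions where fluid can be absorbed".

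**What is measured on the trunk.** The Section 6.8 exam grades "presence of edema at Sites 1-6 (where circumferential measurements were taken", at Baseline and Follow-up. Section 6.7 makes Site 5 the hips and defines "Site 6=narrowest part of the waist", so pitting grade and girth are both taken there. Hip and waist girth belong to the primary objective (Section 3.0) and are analysed by site as well as in a composite (Section 4.1). Trunk ECW/TBW is an exploratory endpoint, also taken at both visits.

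**What is recorded as safety.** Section 6.11.4 describes venous, lymphedema and lipedema complications, "including cellulitis, lymphangitis, deep vein thrombosis, skin breakdown, lymphorrhea, and lymphangiosarcoma". Section 6.11.2 sends device-related adverse events to the AE log, and Section 6.11.1 adds serious adverse events. Table 1 schedules a combined adverse event, complication and device observation assessment at both visits. The patient symptom scale in Appendix E covers the two legs and adds that "these questions are not asking about other parts of your body".

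**What is analysed.** Section 4.1 defines the girth result as a percent reduction and the ECW/TBW result as a mean reduction. Section 13.2 describes no safety analysis of increases at the hip, waist or trunk.

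**The concern.** The treatment is meant to move fluid out of the legs, and the sponsor itself names swelling in the adjoining regions as a possible harm. Whether that harm occurs is therefore a direct safety question, and leg results alone do not answer it.

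Two gaps follow. The first is the genital region, which the protocol text mentions only in the risk list. No exam site, questionnaire or named complication covers it, although cellulitis, in the same risk tier, is a named complication. If a subject is never asked, the answer cannot be recovered at analysis, and a count of zero would be hard to interpret.

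The second is the trunk. The data will exist, but the plan looks at girth and ECW/TBW only for improvement. An increase at the hip or waist, or in trunk ECW/TBW, would appear as a poor efficacy result, and nothing directs that it be reported as a possible harm.

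**Working it through.** There is no plan figure to reproduce: the documents state no rate for this event and no detection target.

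**1. Coverage, place by place**

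| Source | Trunk | Genital region |
|---|---|---|
| Pitting grade, Sites 1-6 (6.7, 6.8) | hips and waist, both visits | not a site |
| Girth (6.7) | hips and waist, both visits | not a site |
| ECW/TBW (4.1, 6.6) | trunk segment, both visits | no separate measure |
| Symptom scale (Appendix E) | outside its scope | outside its scope |
| Named complications (6.11.4) | edema not named | edema not named |
| General assessment (Table 1, 6.11) | possible | possible |

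The trunk has three structured measures. The genital region has only the last row.

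**2. Capture by arm.** Serious events are recorded whatever their cause. A non-serious event reaches the AE log through Section 6.11.2 only if it is associated with Flexitouch Plus use. A control subject has no home device to which it could be attributed. The complication log is not tied to the device and could take a control-arm case, but nothing prompts for one.

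**3. Chance of recording no case.** Inputs: n = 15 device-arm subjects (the analyzable target in Section 13.1), true rate p (assumed) and fraction of cases captured c (assumed). P(no case recorded) = (1 − p × c)^15.

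| p | c = 1 | c = 0.5 |
|---|---|---|
| 5% | 0.95^15 = 46% | 0.975^15 = 68% |
| 10% | 0.90^15 = 21% | 0.95^15 = 46% |
| 20% | 0.80^15 = 3.5% | 0.90^15 = 21% |

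**4. What a zero would mean with everyone asked.** The one-sided 95% upper bound for 0 of 15 is 1 − 0.05^(1/15) = 18.1%.

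**5. Whether the composite can hide a trunk increase.** Assumed girths: eight leg measurements summing to 394 cm, and hip plus waist 228 cm, total 622 cm. Let the legs fall 2% and hip and waist rise 2%.

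- Sum of ten measurements: (0.02 × 394 − 0.02 × 228) / 622 = 3.32 / 622 = 0.53% reduction.
- Mean of ten site percentages: (8 × 2 − 2 × 2) / 10 = 1.2% reduction.
- Hip and waist counted with each leg, as the Section 4.1 wording of six sites per leg could be read: (0.02 × 197 − 0.02 × 228) / 425 = −0.15%, a slight increase.

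So the composite may or may not show benefit while the trunk enlarges, depending on a construction that the plan leaves open. The separate hip and waist results would show the enlargement in every case.

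**The case against.** The strongest reply is that the plan already looks for displaced fluid. A reader might infer from the risk list and the leg-focused scale that no form asks about trunk or genital swelling, and that the trial cannot tell clearance from displacement. For the trunk the documents contradict this: pitting grade, girth and ECW/TBW are taken at both visits, and hip and waist are separately analysed primary sites. Fluid that enlarged the hips or waist would worsen those results.

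A reader might also infer that genital edema is recorded only if the woman volunteers it. That is not established. The AE, complication and exam forms are not reproduced, the Section 6.11.4 list is open-ended, Section 6.8 includes unspecified clinical symptoms, and Table 1 schedules an assessment at both visits. The documents do not say whether that assessment is prompted. What can be said is that the protocol text specifies no targeted item.

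Appendix E does not tell women to withhold other symptoms; it sets the scope of twelve efficacy items. Section 2.3.1 describes fluid going to regions where it is absorbed, and does not say that it causes edema there. The event is in the less-likely tier, and in a study this small asking cannot exclude it: at a 5% rate, full capture still misses every case 46% of the time. Finally, this is a small exploratory study of a marketed device used on label.

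These replies narrow the point. They do not supply a genital edema item, comparable recording in the control arm, or a safety reading of the trunk data.

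**Conclusion.** The point holds as a data-capture gap for genital edema and a reporting gap for the trunk. It is a cheap improvement worth making, and does not threaten the primary analysis.

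Under the assumed rates of 5% to 20%, capturing half the cases instead of all of them raises the chance of recording none by 17 to 25 percentage points (46% to 68%, 21% to 46%, 3.5% to 21%). Both the rates and the capture fraction are assumptions, and actual capture under the general assessment is unknown. A solicited item would make a zero mean asked and denied. It would not rule out a moderate rate, given the upper bound of about 18%.

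The composite calculation rests on assumed girths and shows only why trunk increases should be reported separately from the total.

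**What to change.** 1. In Section 6.11.4 and the Table 1 assessment row, add new or increased genital edema as a solicited yes/no item on the Complication & Healthcare Utilization log, put to every subject in both arms at Baseline and Follow-up. The Baseline answer records existing edema and should be taken before the randomization envelope is opened. A matching trunk item is optional, since the trunk is already measured.
2. In Section 13.2, state that the item will be reported by arm with numerators and denominators, without regard to device attribution.
3. In the same place, state that increases at hip and waist and in trunk ECW/TBW will be reported by arm beside it, separately from the composite circumference total.

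The cost is one or two questions on an existing log at visits already scheduled, and a short table. No examination is added. There are two downsides. Asking will raise recorded counts. Answers at Follow-up may also differ by arm through expectation, because the envelope is opened in front of the subject (Section 6.5) and no blinding is described. The graded and measured trunk data, set beside the answers, help in reading any trunk item, but there is no such check for the genital item.

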8.2 Procedure Risks

All procedures and instruments used in this study are part of standard care. The Inbody 770 sends a minute current identical to current technology used on gym equipment, home scales, non-invasive heart monitors, watches, Fitbit monitors, and the like. This technology is considered extremely safe with no known risks to patient health.

8.3 Risk Mitigation

Subjects will be made aware of known complications and adverse events at the time of consent and monitored closely throughout the study. Subjects will be informed of any significant new findings that develop during the course of the study that may affect their willingness to continue participation. Should a subject choose to

terminate his or her participation in the study, he or she will be treated according to the standard of care that applies at the point of withdrawal.

The Investigator and study team will oversee all safety aspects and report adverse events to the IRB, as required. Should a subject choose to terminate his or her participation, he or she will be treated according to the standard of care that applies at the point of withdrawal.

8.4 Potential Benefits

While there is no guarantee of a direct benefit to participants, there is a possible benefit of improved quality of life and relief of symptoms with use of the Flexitouch Plus.

9.0 Provisions to Protect the Privacy of Study Participants/Information Security Plan

The most likely risk posed to participants would be a breach of confidentiality if someone other than the research team obtained access to the data.

There are security measures in place to prevent a breach of confidentiality from happening including password protected electronic database and the use of subject codes to de-identify data).

Precautions will be taken to make sure that only authorized individuals will be accessing subject research records. The collection of sensitive information about subjects is limited to the amount necessary to achieve the aims of the research, so that no unneeded sensitive information is being collected.

10.0 Deviation from Study Plan

All deviations will be documented on the Deviation Log and reported to the IRB as required by IRB policies.

11.0 Quality Assurance Procedures

This study will be conducted in accordance with Good Clinical Practice (GCP), Code of Federal Regulations (CFR), institutional research policies and procedures, and other appropriate regulatory requirements to ensure subject safety and quality of clinical procedures related to the conduct of the clinical trial. As required by United States Food and Drug Administration (FDA) 21 CFR 56 and the Declaration of Helsinki, the protocol, amendments, and Informed Consent form will be reviewed and approved, according to 21 CFR §50 and §56, by each center's IRB.

11.1 Data Safety Monitoring

The Investigator will be responsible for the monitoring of study data and subject safety. Due to the small number of research subjects, the most comprehensive and effective method of monitoring will be an individual case review by the Investigator (or designee). The Investigator will be made aware of all serious and device-related adverse events; therefore, the responsibility for reporting adverse events is shared with the Investigator and research team.

11.2 Reports and Records

Records to be maintained by the Investigator in a designated study file include:

- Investigational plan and all amendments;
- IRB approval letter, including a copy of the approved consent forms, progress reports, and adverse event reports;
- IRB roster or Assurance number, if applicable;
- All correspondence relating to the conduct of this study between the site, IRB, Tactile Medical, and study monitor;
- Curriculum Vitae and professional license for key study personnel, if applicable;
- Site personnel signature and documentation regarding the Investigator’s delegation of responsibility;
- Protocol/device related training records for all applicable study personnel;
- Screening log; and
- Reports (shown below).

The Investigator is required to prepare and complete reports on this investigation as required by regulations (Table 2).

Table 2. Required Reports

Reports	Submit To	Timeframe
SAE	Tactile Medical	10 business days of becoming aware.
	Reviewing IRB	In accordance with IRB procedure.
Progress Report	Tactile Medical Reviewing IRB	Annually, at a minimum.

The following records must be maintained for each subject enrolled:

- Original, signed and dated informed consent form, as well as documentation of the process of consent;
- Completed CRFs, source document worksheets, and data clarification forms, as applicable; and
- Complete medical records including procedure reports, lab reports, etc., as applicable

Subject study records, correspondence files, all supporting study documentation, and reports will remain on file for a minimum of six years after the conclusion of this study.

12.1 Change to Investigational Plan

Should changes in the study plan or protocol become necessary during the course of the clinical research study, proposed changes will be appropriately reviewed and approved by the IRB before any changes are implemented. All changes must be documented.

13.0 Statistical Methods

13.1 Sample Size Determination

The study is not formally powered for a specific primary hypothesis, thus no formal power/sample size estimation was performed. The study sample size was determined based upon a desire to be able to estimate the means of the primary within group endpoints, using 95% confidence intervals, with the estimation of the endpoint means to have a precision (half width of the confidence intervals) of approximately 40% of the observed standard deviation. To achieve these parameters, we have determined a target analyzable sample size of 15 subjects (30 total legs as the observational units) per group. To accommodate an expected attrition rate of up to 20%, a total of 3 subjects per arm will be replaced, if they fail to fully complete the study.

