4.1 Endpoint Mapping

Endpoint	Outcome Measure	Analysis
Primary	
 Circumferential Measurements 	
 Calculate percent reduction at Follow-up compared to Baseline for 6 sites on each leg as well as a composite total.
Primary	
 Quality of Life 	
 Compare Follow-up RAND SF36 score to Baseline.¹
Primary	
 Symptoms & Pain Intensity 	
 Compare Follow-up PROMIS Pain Interference², Wong-Baker Faces Scale, and the NIH Toolbox numerical rating scale (NRS) scores to Baseline.
Exploratory	
 Mobility 	
 Compare Follow-up PROMIS Mobility score to Baseline.²

¹ https://www.rand.org/health-care/surveys_tools/mos/36-item-short-form/scoring.html

² http://www.healthmeasures.net/index.php?option=com_instruments&task=Search.pagination&Itemid=992

Endpoint	Outcome Measure	Analysis
Exploratory	
 • Bioimpedance Measurements 	
 • Calculate mean reduction at Follow-up compared to Baseline for the Segmental (Right/Left Arm/Leg, Trunk) and Whole Body Extracellular Water (ECW)/Total Body Water (TBW) ratios.

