6.9.1 QOL

The RAND 36-Item Health Survey (Version 1.0) taps eight health concepts: physical functioning, bodily pain, role limitations due to physical health problems, role limitations due to personal or emotional problems, emotional well-being, social functioning, energy/fatigue, and general health perceptions. It also includes a single item that provides an indication of perceived change in health. (*Appendix A*)

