6.9.3 Pain Interference & Symptoms

To assess pain and symptoms related to lipo-lymphedema (lipedema with swelling), subjects will complete:

- The PROMIS Pain Interference - Short Form 6b v1.0 (2 May 2016) measures self-reported consequences of pain on relevant aspects of a person's life and may include the extent to which pain hinders engagement with social, cognitive, emotional, physical, and recreational activities. (*Appendix C*)
- The Wong-Baker Faces Pain Rating Scale is a pain scale that shows a series of faces ranging from a happy face at 0, or "no hurt," to a crying face at 10, which represents "hurts like the worst pain imaginable." Based on the faces and written descriptions, the patient chooses the face that best describes

their level of pain associated with lipo-lymphedema (lipedema with swelling). (*Appendix D*)

- Subjects will be asked to rate their perceptions of swelling, heaviness, pain, fatigue, tenderness, and tightness independently for each leg using a 10-point numerical rating scale where 0 represents none/not present and 10 is worst imaginable.³ (*Appendix E*)

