13.2 Statistical Analysis

For continuous variables, descriptive statistics will include the number of subjects (n), mean, standard deviation, median, inter-quartile range, minimum, and maximum, based upon subjects with reported data for the variable being analyzed. Frequencies (numerator and denominator), percentages, and 95% confidence intervals will be displayed for categorical data. Percentages by categories will be based on the number of subjects with no missing (unreported) data for the specific variable being analyzed and the count of the patients for each individual level of the categorical variable (the level specific numerators). Percentages will add up to 100%, unless otherwise indicated.

There are no plans to impute missing data and there are no plans to explicitly report missing data (counts and/or percentages) in the tables for all variables as part of the planned study report content. Variations in the reported sample sizes within and/or between relevant tables can be used to ascertain insights into unreported data. In some cases, unreported data may be due to it not being clinically relevant to a particular patient or may represent expected data that was not collected. Selected analyses pertaining to unreported and/or missing data may be discussed and considered as future findings warrant.

The exploratory nature of the study suggests that the statistical focus will be on estimation and hypothesis generation and not hypothesis testing. Though p-values will be reported as apropos, point estimates, and 95% confidence intervals will be used to guide exploratory analyses for potentially clinically meaningful differences or changes to be discussed and evaluated.

Primary within treatment group analyses of change from baseline will utilize paired tests (e.g. paired t-tests, McNemar chi-square) or similar non-parametric tests as appropriate, to compare the 30-day measurement to baseline.

Secondary between treatment group comparative analyses of change from baseline will utilize ANCOVA or similar methods as appropriate. These methods will include the 30-day measurement as the dependent (response) variable, while the baseline measurement and treatment group will be the independent variables. Assessments of any interactions between the baseline measurement and treatment group will be performed.

Other exploratory comparisons, when performed, will utilize chi-square, ANOVA, t-test, and appropriate non-parametric tests, unless otherwise specified.

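### The precision of about 0.40 SD in section 13.1 rests on counting 30 legs; primary endpoints with one value per subject have n = 15 and about 0.55 SD, and 13.2 states no unit for leg data

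*Combined protocol and SAP*

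**What the plan says.** Section 13.1 disclaims a power calculation and bases the size on estimating the primary endpoint means within each group. The target is a "precision (half width of the confidence intervals) of approximately 40% of the observed standard deviation", using 95% intervals. To meet it, "we have determined a target analyzable sample size of 15 subjects (30 total legs as the observational units) per group". The target is not restricted to leg measurements, and no correlation between a subject's two legs is given.

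The primary endpoints in section 4.1 are of two kinds.

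- **One value per subject.** Quality of life ("Compare Follow-up RAND SF36 score to Baseline"), where section 6.9.1 explains that "The RAND 36-Item Health Survey (Version 1.0) taps eight health concepts", so each scale gives one score per subject. PROMIS Pain Interference. Wong-Baker, where "the patient chooses the face that best describes" the pain (section 6.9.3). Hip and waist circumference, each taken once (section 6.7).
- **One value per leg.** Circumference sites 1 to 4 (section 6.7) and the symptom ratings: "Subjects will be asked to rate their perceptions of swelling, heaviness, pain, fatigue, tenderness, and tightness independently for each leg" (section 6.9.3).

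In section 13.2, "descriptive statistics will include the number of subjects (n), mean, standard deviation", so the count there is of subjects. Change within a group is tested with paired tests or non-parametric equivalents. Groups are compared by ANCOVA or similar methods, with baseline and treatment group as the independent variables. No unit of inference is given for leg data. The section also says that "the statistical focus will be on estimation and hypothesis generation and not hypothesis testing".

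**The concern.** Precision is the only justification offered for 15 subjects per group, and section 13.2 relies on point estimates and 95% intervals to judge which changes may matter clinically. If the promised width depends on counting legs, it cannot apply to a questionnaire completed once per subject. Readers would then expect narrower intervals than the study can produce for much of its primary endpoint list.

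The second issue is the unit for leg data. Section 13.1 calls legs the observational units, section 13.2 counts subjects, and neither says how two correlated values from one person are to be handled. The two sections therefore leave open an analysis that treats the legs as independent, whose intervals would be too narrow.

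**Working it through.** **Inputs.** From 13.1: 95% confidence, target half-width about 0.40 of the observed SD, 15 subjects or 30 legs per group. From 4.1, 6.7, 6.9.1 and 6.9.3: which endpoints have one value per subject and which have one per leg. Assumed, because the documents do not give it: rho, the correlation between the left and right changes of one subject.

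**Step 1: the plan's own figure.** The half-width in SD units is q/√n, with q the t quantile on n − 1 df or z = 1.960. With n = 30 independent values:

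- t: t(0.975, 29)/√30 = 0.373
- z: 1.960/√30 = 0.358

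Both fit the stated figure of about 0.40. In reverse, 0.40 needs 25 (z) or 27 (t) independent values. So 30 legs reproduce the claim.

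**Step 2: one value per subject.** With n = 15:

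- t: 2.145/√15 = 0.554, and 0.554/0.40 = 1.38
- z: 1.960/√15 = 0.506, and 0.506/0.40 = 1.27

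The target is expressed relative to the observed SD, so for a t interval this ratio depends on n alone. Rho plays no part. Even 18 analysed subjects per group (15 plus the 3 replacements) would give 0.497 by t or 0.462 by z.

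**Step 3: leg endpoints.** The mean over 15 subjects with two legs each has variance (1 + rho)/30 in units of the single-leg variance. The half-width is therefore q·√((1 + rho)/30), with q = 2.145 (t, 14 df) or 1.960 (z). Setting this to 0.40 gives the largest admissible rho, 30·(0.40/q)² − 1:

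- z: 0.25
- t: 0.04

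The coverage column below applies only if 30 legs are pooled as independent. It comes from simulating the within-group interval for 15 subjects with two legs each (400,000 replicates).

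| Assumed rho | Half-width, single-leg SDs (t, 14 df) | Same by z | Coverage of nominal 95% interval if legs are pooled |
|---|---|---|---|
| 0 | 0.392 | 0.358 | 95.1% |
| 0.3 | 0.446 | 0.408 | 91.5% |
| 0.5 | 0.480 | 0.438 | 88.9% |
| 0.8 | 0.525 | 0.480 | 85.0% |
| 0.9 | 0.540 | 0.493 | 83.7% |

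In the same simulation the per-subject mean of two legs kept 95.0% coverage at every rho, and one leg analysed alone kept 95.0% to 95.1%.

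**Step 4: leg endpoints as subject means.** The mean of two legs has SD √((1 + rho)/2) single-leg SDs. Relative to its own observed SD, its half-width is again 2.145/√15 = 0.554, whatever rho is.

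**The case against.** The best defence is that the parenthesis in 13.1 names legs, so the precision sentence may be meant only for the leg-level endpoints. On that reading the arithmetic for 30 values is right and the fault is one of scope. This is fair as far as it goes: the figure does reproduce from 30 values. But 13.1 speaks of the primary endpoints without limit, and the leg-only reading still needs legs that are nearly uncorrelated. By z there is some room (rho up to 0.25), by t almost none (0.04), and 13.1 does not say which quantile was used or justify independence.

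It can also be said that the target is approximate, that the study is exploratory, and that no power claim is made. All true, and they limit the consequence. They do not make 0.51 to 0.55 approximately 0.40.

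A reader might infer that the leg analyses will produce intervals with 84% to 91.5% coverage. The documents do not support that. Section 13.2 never says legs will be pooled, it counts subjects, it allows similar methods as appropriate, and 4.1 can be read as separate left and right results. The coverage figures describe one analysis that the text leaves open. Nor is this a failed power calculation, since 13.1 made none. Intervals for endpoints with one value per subject remain valid; only the forecast of their width is wrong.

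**Conclusion.** The precision statement in 13.1 is wrong as written. For primary endpoints with one value per subject, 15 subjects give a half-width of about 0.55 of the observed SD by t (0.51 by z), not about 0.40. This needs no correlation assumption, only that 13.1 covers the primary endpoints it refers to.

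For leg endpoints the conclusion depends on rho. About 0.40 of a single-leg SD is available only when left and right changes are nearly uncorrelated; by t the half-width is 0.45 to 0.54 for assumed rho of 0.3 to 0.9.

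The unit of inference for leg data is unstated. If, and only if, 30 legs per group were pooled as independent, a nominal 95% within-group interval would cover about 91.5% at rho 0.3, 89% at 0.5 and 84% at 0.9.

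This should be fixed, but it does not invalidate the design.

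**What to change.** **Section 13.1.** Make the subject the unit and delete the parenthesis that names legs as observational units. Restate the precision as about 0.55 of the observed SD (t, n = 15), both for endpoints with one value per subject and for leg endpoints analysed as the per-subject mean of both legs. Any figure in single-leg SDs should say so and give its assumed rho.

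**Section 13.2.** Name the per-subject mean of the two legs as the single primary method for leg data, within groups and in the ANCOVA, with the mean baseline as covariate. A model with a subject term can serve as a sensitivity analysis. It is not equivalent in an ANCOVA with a leg-level baseline: in 40 simulated trials of 30 subjects (assumed baseline leg correlation 0.7, residual correlation 0.5) the two treatment estimates differed by up to 0.106, against a standard error of about 0.16. They also diverge when one leg is missing, and no imputation is planned. Analyse hip and waist once per subject. If left and right are reported separately, state n = 15 for each.

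**Cost.** Wording only, and no extra patients. The price is a less favourable stated precision. For information, keeping 0.40 SD with one value per subject would take 25 (z) to 27 (t) analyzable subjects per group.

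As a separate minor point that adds no weight here, 4.1 counts six sites on each leg while 6.7 lists ten measurements in all (four per leg, one hip, one waist). The two should be reconciled when the composite is defined.
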